## CONFIDENTIAL

**This protocol may not be reproduced or communicated to a third party without the written permission of Grünenthal GmbH.**

## SUMMARY OF CHANGES

**Amendment Type:** Substantial

**Rationale for Amendment:** The protocol tries to avoid the inclusion of patients who are on chronic treatment with drugs known to interfere with wound healing and/or are known to trigger wound healing complications like haematoma. Unfortunately, the chosen phrase in Version 3.0 of the protocol prohibits the application of steroids, immunosuppressants, chemotherapy, or anticoagulants with the exception of anti-platelet therapies pre-operation and also post-operatively. This was never intended and indeed would be against established deep vein thrombosis prophylaxis regimens, neo-adjuvant chemotherapies etc. The proposed amendment of the protocol corrects this aspect.

**Summary of Amendment:** See below.

Section	Change Made	Rationale for Change
Cover page and header	Protocol version and date changed to v4.0, 25 Feb 2019.	
Protocol Approval Signature page	Change of one of the CRO signatories from [REDACTED] to [REDACTED]	
Synopsis and Section 7.3.3	
Exclusion Criterion #8
 
Subjects requiring suturing with sutures <del>>5-0</del> 0.5 mm thickness
 
Exclusion Criterion #12 Subjects receiving chronic, pre-operative steroids, immunosuppressants, chemotherapy, or anticoagulants; only chronic anti-platelet therapies like ASA and clopidogrel are accepted. Chronic is to be interpreted as long term or “for more than acute treatment”. Pre-operative standard of care, like a single dose of an anticoagulant, for the aforementioned treatments is allowed along with standard of care post-operative anticoagulant and chemotherapy regimen including application of steroids and immunosuppressants.
	
Clarification to avoid confusion which arose from the use of a USP and metric combination to describe the suture thickness.
 
To allow application of steroids, immunosuppressants, chemotherapy, or anticoagulants with the exception of anti-platelet therapies pre-operatively and post-operatively, to be in line with established deep vein thrombosis prophylaxis regimens, neo-adjuvant chemotherapies, etc.

Section 7.4.8.1	Prohibited medications are chronic ,	To allow application of

Section	Change Made	Rationale for Change
Prohibited Medication/Therapy	
pre-operative steroids, immunosuppressants, chemotherapy, and anticoagulants; only chronic anti-platelet therapies like acetylsalicylic acid (ASA) and clopidogrel are accepted. Chronic is to be interpreted as long term or “for more than acute treatment”. Pre-operative standard of care, like a single dose of an anticoagulant, for the aforementioned treatments is allowed along with standard of care post-operative anticoagulant and chemotherapy regimen including application of steroids and immunosuppressants.
	
steroids, immunosuppressants, chemotherapy, or anticoagulants with the exception of anti-platelet therapies pre-operatively and post-operatively, to be in line with established deep vein thrombosis prophylaxis regimens, neo-adjuvant chemotherapies etc.

Throughout protocol	
Corrections to typographical and grammatical errors.
	
To improve readability.

## 2 SYNOPSIS

### Protocol Number:

KF7021-04

### Title:

A randomized, open-label, multi-center, controlled clinical study to compare MAR-CUTIS with Dermabond Advanced in closure of surgical incisions and lacerations  $\leq 15$  cm.

### Investigational Device:

MAR-CUTIS topical tissue adhesive

### Study Centers:

Up to 22 study centers located in the European Union

### Phase:

Pivotal

### Investigational Device Management Category:

European Union: IIb; United States: II

### Study Design:

This is a randomized, open-label, multi-center, comparator-controlled clinical study to compare MAR-CUTIS with Dermabond Advanced in closure of surgical incisions  $\geq 6$  to  $\leq 15$  cm and lacerations  $\leq 15$  cm. Eligible subjects will be randomized 2:1 to MAR-CUTIS or Dermabond Advanced.

### Number of Subjects:

A total of 189 subjects will be treated (defined as study product applied to the wound). Only subjects that are withdrawn from the study due to product failure at the time of application will be replaced. Re-screening is not allowed in the study.

### Treatment:

MAR-CUTIS or Dermabond Advanced topical tissue adhesive will be applied to surgical incisions  $\geq 6$  to  $\leq 15$  cm and lacerations  $\leq 15$  cm as a last dermal closing layer on Day 0 once wounds have been prepared in a standard manner.

### Study Duration:

The overall study duration for each subject is up to 4 months:

- Day -21 to Day 0: screening, presurgical examination.
- Day 0: presurgical examination, surgery, final eligibility, allocation to treatment group, treatment.
- Follow-up visits: Day 1, Day 10, Month 1, and Month 3 or Early Discontinuation.

### Study Population:

#### Inclusion Criteria

For subjects with surgical incisions:

1. Subject undergoing closure of surgical incision  $\geq 6$  to  $\leq 15$  cm following a laparotomy, abdominal hysterectomy, inguinal hernia repair, or laparoscopic intervention.

For subjects with lacerations:

2. Subject requiring closure of a laceration on face (avoiding the immediate area around the eye or lips/mouth) or extremities,  $\leq 15$  cm. In subjects with multiple lacerations, one will be selected as the target wound (ie, greatest length and meets the study entry criteria).

For all subjects:

- 
3. Subject has the ability to consent and has given written informed consent/assent to participate.
  4. Male and female subjects  $\geq 2$  years of age and body weight  $\geq 10$  kg.
  5. Subject willing and capable of following instructions for wound care provided by the investigator and agreeing to return for all treatment control visits specified in this clinical study.

### Exclusion Criteria

For subjects with lacerations:

1. Wounds on mucosal surfaces or across mucocutaneous junctions (eg, oral cavity, lips, eyes).
2. Wounds which may be regularly exposed to body fluids or with dense natural hair (eg, scalp); wounds on ears.
3. Wounds on palms and feet.
4. Animal or human bites.
5. Lacerations that are heavily contaminated.
6. Punctured or crushed wounds.
7. Subjects with lacerations having wound treatment  $>6$  hours after the trauma.

For all subjects:

8. Subjects requiring suturing with sutures  $>0.5$  mm thickness.
9. Subject with documented skin disease or skin conditions (eg, excessive hair at the site of surgery, scar tissue, wound, tattoo, coloration, or pre-existing open sores at the site of surgery that would interfere with the application of investigational medical device [IMD] or the skin assessment, as judged by the investigator).
10. Subject with any factors that may have an adverse effect on wound healing (eg, previous history of keloid formation or hypertrophy [including family history]), other general risk factors for dehiscence (need of premature post-surgery exercise/heavy lifting, expected conditions leading to recurrent vomiting, coughing, or constipation), history of immunosuppression, chronic systemic infection, or poor general health.
11. Subjects with known blood clotting disorders.
12. Subjects receiving chronic, pre-operative steroids, immunosuppressants, chemotherapy, or anticoagulants; only chronic anti-platelet therapies like acetylsalicylic acid (ASA) and clopidogrel are accepted. Chronic is to be interpreted as long term or “for more than acute treatment”. Pre-operative standard of care, like a single dose of an anticoagulant, for the aforementioned treatments is allowed along with standard of care post-operative anticoagulant and chemotherapy regimen including application of steroids and immunosuppressants.
13. Subject having known or suspected allergy or sensitivity to polyurethane, cyanoacrylates, formaldehyde, tapes or adhesives, or benzalkonium chloride.
14. Subject participating in any current clinical study with a non-Conformité Européenne–marked device or investigational product.
15. Subject who is pregnant or breastfeeding.
16. Subject with history of a significant dermatologic disease or condition, such as atopic dermatitis, psoriasis, lichen ruber planus, vitiligo or conditions known to alter the skin appearance or physiologic response (eg, decompensated diabetes mellitus, porphyria) that involves the investigative site.

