### **7.4 Investigational Medical Device**

#### **7.4.1 Investigational Medical Device Applied**

MAR-CUTIS is a polyurethane-based skin adhesive. At the time of use, the 2 components in the syringe are mixed in the mixing cannula. Complete hardening occurs about 5 minutes after application to the skin. The adhesive result can be corrected in the first 30 seconds. MAR-CUTIS is distributed sterile and is intended for single use. The product is used for topical closure of incisions and surgical wounds, replacing the last dermal suture line. It is not intended for intra-abdominal use and/or as a substitute for subcutaneous sutures. It should not be used after the expiration date and/or if the sterile packaging has been opened or damaged.

Dermabond Advanced is a topical skin adhesive used to hold closed easily approximated skin edges of wounds from surgical incisions, including incisions from minimally invasive surgery, and simple, thoroughly cleansed, trauma-induced lacerations.

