#### **7.4.2 Identity of Investigational Medical Device**

The prepolymer component of MAR-CUTIS is made with hexamethylene diisocyanate, benzoyl chloride, and trifunctional polyol with primarily short alkylene oxide units. The curing agent is composed of diethyl maleate, 1,5-diamino-2-methylpentane, and polyethylene glycol 200. MAR-CUTIS should be stored at room temperature (15 to 25°C) and should be protected from moisture and humidity.

The active ingredient in Dermabond Advanced is 2-octyl cyanoacrylate. The recommended storage conditions are below 30°C (86°F), and away from moisture, direct heat, and direct light.

---

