### 7.4.4 Method of Assigning Subjects to Treatment Groups

Subjects (ie, the unique subject identifier [ID] consisting of center ID and subject ID) will be randomly allocated to treatment according to a randomization scheme designed using the covariate-adjusted dynamic allocation method as implemented in Balance (Medidata, 2015). The algorithm combines complete randomness with a minimization method (Pocock and Simon, 1975), not only looking at marginal balances, but also considering the treatment balances overall and within individual strata, to ensure a balanced treatment allocation. Based on the expected clinical relevance of the explanatory variables for incision and laceration closure, the algorithm is implemented by assigning a different weight to the stratification factors to be included in the trial and minimize unbalances (ie, wound type having more importance than the other 2 factors, and age group having more importance than skin type). Further details regarding the parameters used to implement the randomization in balance are documented in the form “Balance Study Configuration Requirements”.

The incision/laceration will be prepared for closure as per the standard of care at a treating hospital. The investigator will assess the need and perform closure of deep tissue layers as necessary before proceeding with the randomization and subsequently with the closure of the last (dermal) layer with the IMD.

Eligible subjects will be randomized 2:1 to MAR-CUTIS or Dermabond Advanced.

The study will include 3 levels of stratification as randomization factors:

- By wound type (lacerations and incisions).
- By skin type according to the Fitzpatrick classification (types I to III versus types IV to VI).
- By age group (aged 2 to 21 years and  $\geq 22$  years).

The primary efficacy analysis will consider the stratification factors as explanatory variables in the model. Additionally, center will be considered as a further randomization factor as recommended by International Council for Harmonisation (ICH) E9.

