#### CONTRAINDICATIONS

- Do not use on any wound with evidence of active infection, gangrene, or wounds of decubitus etiology.
- Do not use on mucosal surfaces or across mucocutaneous junctions (e.g., oral cavity, lips), or on skin which may be regularly exposed to body fluids or with dense natural hair.
- Do not use on patients with a known hypersensitivity to cyanoacrylate or formaldehyde.

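### Exclusion 13 covers MAR-CUTIS by material class but not by the constituents in Section 7.4.2, so a subject allergic only to a listed constituent is eligible as written

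*Protocol*

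**What the plan says.** Criterion 13 applies to all subjects and appears in the same words in the protocol synopsis and Section 7.3.3: "Subject having known or suspected allergy or sensitivity to polyurethane, cyanoacrylates, formaldehyde, tapes or adhesives, or benzalkonium chloride".

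On the test device, Section 7.4.1 states: "MAR-CUTIS is a polyurethane-based skin adhesive". Section 7.4.2 gives its two parts. For the first: "The prepolymer component of MAR-CUTIS is made with hexamethylene diisocyanate, benzoyl chloride, and trifunctional polyol with primarily short alkylene oxide units". For the second: "The curing agent is composed of diethyl maleate, 1,5-diamino-2-methylpentane, and polyethylene glycol 200". The parts are mixed in the cannula at the time of use, and Section 7.4.1 adds: "Complete hardening occurs about 5 minutes after application to the skin".

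On the comparator, Section 7.4.2 states: "The active ingredient in Dermabond Advanced is 2-octyl cyanoacrylate". The description in its instructions for use (Section 15.2) adds a colorant, D & C Violet #2. The contraindications there include: "Do not use on patients with a known hypersensitivity to cyanoacrylate or formaldehyde".

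On allocation, Section 7.4.4 states: "Eligible subjects will be randomized 2:1 to MAR-CUTIS or Dermabond Advanced".

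**The concern.** An allergy exclusion should stop a subject with a known allergy to something in either product from being randomised to it. For the comparator, both labelled hypersensitivities are carried into criterion 13. For MAR-CUTIS the criterion gives the name of the material class and a general adhesive entry, but nothing from the protocol's own composition list.

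MAR-CUTIS goes onto the skin as a freshly mixed two-part product and hardens there over some minutes. A known allergy to a constituent of the curing agent is therefore relevant at screening. It need not be on record as an allergy to polyurethane or to adhesives.

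Screening and baseline can fall on the same day, and lacerations must be treated within 6 hours of the trauma. Site staff are then likely to rely on the literal text of the criterion. What is at stake is an avoidable reaction in a small number of subjects. Any such reaction would enter the main safety endpoint, adverse events within 1 month classified by severity and relatedness.

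**Working it through.** **Allocation figure.** Section 10.2 gives 126 MAR-CUTIS and 63 Dermabond Advanced subjects: 126 + 63 = 189, and 126 / 63 = 2, which agrees with the 2:1 ratio. The MAR-CUTIS share is 126 / 189 = 0.667, or two in three. This is an average. Allocation is dynamic, by a minimisation method (Section 7.4.4), so the probability for one subject can differ.

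**From criterion to devices.**

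| Entry in criterion 13 | MAR-CUTIS | Dermabond Advanced |
|---|---|---|
| Polyurethane | Material class (7.4.1) | Not listed |
| Cyanoacrylates | Not listed | Active ingredient (7.4.2) and contraindication (15.2) |
| Formaldehyde | Not listed | Contraindication (15.2) |
| Tapes or adhesives | General cover | General cover |
| Benzalkonium chloride | Not listed | Not listed |

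**From devices to criterion.**

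| Listed material | Source | Named in criterion 13? |
|---|---|---|
| Hexamethylene diisocyanate | 7.4.2, used to make the prepolymer | No |
| Benzoyl chloride | 7.4.2, used to make the prepolymer | No |
| Trifunctional polyol | 7.4.2, used to make the prepolymer | No |
| Diethyl maleate | 7.4.2, constituent of the curing agent | No |
| 1,5-diamino-2-methylpentane | 7.4.2, constituent of the curing agent | No |
| Polyethylene glycol 200 | 7.4.2, constituent of the curing agent | No |
| 2-octyl cyanoacrylate | 7.4.2 and 15.2, comparator | Yes, by class |
| D & C Violet #2 | 15.2, comparator | No |

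None of the 6 MAR-CUTIS materials is named. Of the 2 comparator materials, 1 is covered by class. Both of the comparator's stated hypersensitivities are covered.

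**The two MAR-CUTIS parts differ.** For the prepolymer, Section 7.4.2 describes what it is made with. That identifies starting materials and does not show that any remains free in the syringe. Section 5 describes this part as already polyurethane-based. For the curing agent, Section 7.4.2 states what it is composed of, so its three constituents are in the product as dispensed.

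**Other criteria.** The nearest are 9 (skin conditions interfering with application or assessment), 10 (factors impairing wound healing) and 16 (dermatologic disease at the site). None concerns allergy to a device component.

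**Test case.** Take a subject with documented polyethylene glycol allergy and no known sensitivity to polyurethane, adhesives or the other named items. No entry in criterion 13 applies, so the subject is eligible. Of any k such subjects enrolled, about 2k/3 would on average receive MAR-CUTIS. The documents give no value for k.

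**The case against.** The strongest reply is that the test device is covered. Polyurethane is the first item named and is the MAR-CUTIS material, the adhesive entry applies to both products, and the criterion extends to suspected as well as known sensitivity. This stands against any claim that only the comparator's allergens are screened. It does not help with the test case above, where none of those entries applies.

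A reader might also infer a one-sided screen from setting the comparator's contraindications beside the MAR-CUTIS ingredient list. Those are unlike things. On composition, the comparator's colorant is not named either, and the MAR-CUTIS instructions and risk analysis report, which could hold its own contraindications, are not among the documents. The criterion is also applied before randomisation, equally to both arms, and safety is summarised descriptively without tests (SAP Section 14).

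A third tempting inference is that all six listed materials reach the skin. The documents do not establish this for the diisocyanate or benzoyl chloride. They give no residual-monomer data, Section 5 says the adhesive does not react with tissue, and preclinical testing and risks are left to the Investigator's Brochure. This objection stands for the prepolymer inputs but not for the curing agent.

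Finally, the 11.5% rate of allergic reactions in Section 5 was observed with other skin adhesives. It does not measure prior allergy to these constituents and cannot size the gap.

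**Conclusion.** The point holds in a limited form. Criterion 13 covers MAR-CUTIS by class and not by listed constituent, and a subject allergic only to a listed constituent passes it as worded. The case is firm for the three curing-agent constituents and open for the prepolymer inputs.

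The effect is probably small, and its size is unknown because the documents do not say how many candidates would have such an allergy. The only figure that can be attached is the average two-in-three chance of allocation to MAR-CUTIS. The conclusion assumes that sites apply the criterion literally and that no document outside the protocol and SAP adds a component-allergy check.

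A reader might take benzalkonium chloride for a slip for benzoyl chloride, since Section 7.4.2 lists only the latter. The documents cannot show that: the entry could refer to a constituent they do not list. It supports a query to the sponsor and no more.

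**What to change.** Reconcile criterion 13, in both the synopsis and Section 7.3.3, with the compositions in Sections 7.4.2 and 15.2. One way is to keep every present entry and add known allergy to any component of either device, with the constituents set out on the screening checklist so that staff need not look them up. The sponsor should settle the wording against the Investigator's Brochure and the MAR-CUTIS risk analysis report, including whether the prepolymer inputs matter for skin contact. Separately, the sponsor should confirm where the benzalkonium chloride entry comes from, and correct or explain it.

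The cost is one line in an amendment and on the checklist. A few candidates may be excluded. Sample size, allocation and analysis do not change.

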**Withdrawal Criteria:**

Subjects will be withdrawn from the study if the adhesive does not adhere appropriately at the time of application as assessed by the investigator and the event will be reported as device deficiency.

**Objectives and Endpoints:**

Objectives	Endpoints

Primary Efficacy Objective:
 
 
To compare the dehiscence rate between MAR-CUTIS and Dermabond Advanced between Day 1 and Day 10.
 
	
Primary Efficacy Endpoint:
 
 
Total dehiscence rate of target incision/laceration assessed at the Day 10 visit.
 

Main safety objective:
 
 
To compare the incidence of adverse events between MAR-CUTIS and Dermabond Advanced.
 
	
Main safety endpoint:
 
 
Adverse events within 1 month after treatment classified by severity and relatedness to the treatment.
 

Secondary	

 
To compare the dehiscence rate between MAR-CUTIS and Dermabond Advanced at the Month 1 visit.
 
	
 
Total dehiscence rate of target incision/laceration assessed at the Month 1 or Early Discontinuation visit (if Early Discontinuation occurs before Month 1).
 

 
To compare the incidence of adverse events between MAR-CUTIS and Dermabond Advanced at additional study time points.
 
	
 
Adverse events classified by severity and relatedness to the treatment.
 

 
To evaluate the subject satisfaction with the cosmetic outcome after treatment of the surgical incision/laceration with MAR-CUTIS versus Dermabond Advanced
 
	
 
Subject-completed Patient and Observer Scar Assessment Scale (POSAS) done at the Month 1 and Month 3 visits or at the Early Discontinuation visit (if Early Discontinuation occurs before Month 1).
 


 
To compare the wound infection incidence between both treatment groups.
 
	
 
Wound infection incidence assessed at the Day 10, Month 1, and Month 3 visits or at the Early Discontinuation visit (diagnosed according to the Centers for Disease Control and Prevention criteria for surgical site infection).
 
Wound infection assessed on a binary scale (“1 - yes” or “0 - no”) for the following criteria: 
 
Presence of erythema
 
Presence of edema
 
Presence of pain at rest
 
Presence of elevated temperature
 
 
 
 
A total score will be calculated for each subject.

 
To evaluate the investigator satisfaction with the cosmetic outcome after the closure of the target surgical incision/laceration with MAR-CUTIS versus Dermabond Advanced.
 
	
 
Investigator-completed POSAS done at the Month 1 and Month 3 visits or at the Early Discontinuation visit.
 
Investigator-completed Modified Hollander Cosmesis Scale (mHCS) done at the Day 10 and Month 1 visits or at the Early Discontinuation visit (if Early Discontinuation occurs before Month 1).
 

 
To evaluate the subject comfort with the device during and after treatment with MAR-CUTIS versus Dermabond Advanced.
 
	
 
A questionnaire related to subject experience and satisfaction with the device completed by the subject at the Day 10 and Month 1 visits or at the Early Discontinuation visit (if Early Discontinuation occurs before Month 1).
 
A subject-related questionnaire to be completed by investigators at the Day 0 and Month 1 visits or at the Early Discontinuation visit (if Early Discontinuation occurs before
 

Objectives	Endpoints

 
To evaluate the investigator overall satisfaction and ease of use with the device during and after the closure of the target surgical incision/laceration with MAR-CUTIS or Dermabond Advanced.
 
	
Month 1).
 
 
A product-related questionnaire completed by investigators at the Month 1 or Early Discontinuation visit (if Early Discontinuation occurs before Month 1).
 

